Our novel sleep optimization intervention employs: a wearable sleep tracker, didactic content, an interactive smartphone application, and brief telephone counseling.⁹ For this proposal, we will adapt the intervention to be T1D-specific. We will then test preliminary efficacy. We hypothesize T1D-Sleep-Opt-In will be feasible and acceptable and increase sleep duration and regularity; results will serve as pilot data for a larger trial (RFA-DK-17-028 *Treating Diabetes Distress to Improve Glycemic Outcomes in T1D*). This pilot study will randomize 20 working adults with T1D (18-65 years) who report habitual short sleep duration to eight-week T1D-Sleep-Opt-In or attention control. **Specific aims** are to determine:

Aim 1: Feasibility and acceptability of T1D-Sleep-Opt-In. **Rationale:** Analysis of recruitment, retention, and participant program evaluation will provide feasibility and acceptability data. **Hypothesis:** T1D-Sleep-Opt-In will be feasible and acceptable to the target population. **Approach:** Feasibility will be determined through analysis of recruitment and retention. Acceptability will be determined through participant evaluation.

Aim 2: Preliminary efficacy of T1D-Sleep-Opt-In on sleep duration and regularity. **Rationale:** Our sleep optimization intervention resulted in increased sleep duration in non-T1D individuals. **Hypothesis:** T1D-Sleep-Opt-In will result in clinically significant increased sleep duration and regularity. **Approach:** Sleep duration and regularity will be measured by actigraphy at baseline, Week 4, Week 8, and post-program at Weeks 12 for both groups (and Week 24 T1D Sleep-Opt-In only).

Aim 3: Preliminary efficacy of T1D-Sleep-Opt-In on glycemic control. **Rationale:** Short sleep duration and sleep irregularities were associated with poor glycemic control in T1D. Sleep optimization in short-sleeping individuals without diabetes resulted in improved insulin resistance. **Hypothesis:** T1D-Sleep-Opt-In will result in improved glycemic control. **Approach:** A randomized controlled trial of an 8-week T1D-Sleep-Opt-In compared to an information control group on glycemic control, measured by A1C, fructosamine, and glucose variability from continuous glucose monitoring assessed at baseline, Weeks 4, 8, and post-program Week 12 for both groups (and Week 24 T1D Sleep-Opt-In only).

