Our data and others' reveal that diabetes distress is associated with higher A1C and glycemic variability in T1D.^{6,33} Diabetes distress is associated with poor self-care behaviors such as dietary/medication non-compliance^{34,35} and physical inactivity.³⁵ Thus, diabetes distress can be a barrier in improving glycemic control.³⁶ Interventions using diabetes-self management education or in a combination with psychological components reported reductions in diabetes distress and improved glycemic control in some^{6,37-40} but not all studies.^{6,41} No studies to date explored the effects of sleep intervention on diabetes distress.

A.4 Sleep optimization is feasible and shown to improve glucose metabolism in short sleepers.

The goal of this application is to examine the feasibility and preliminary efficacy of a sleep optimization intervention for glycemic control and diabetes distress in T1D. Despite strong data to support a causal relationship between insufficient sleep and abnormal glucose metabolism, few studies have explored sleep interventions as a means to improve metabolic outcomes. Only one published study examined the effects of home sleep extension on glucose metabolism in healthy volunteers ($n = 16$) who were chronic short sleepers.⁴² After six weeks of sleep extension (average increase by 44 minutes/day), there was a robust correlation between the increase in sleep duration and improvement in fasting insulin sensitivity. In our randomized cross-over sleep extension study of 21 short-sleeping non-diabetic working-age adults, those who extended their sleep to > 6h/night for 2 weeks had significant improvement in fasting insulin resistance, early insulin response to glucose, and β -cell function. Another RCT of 42 normal-weight, healthy, short sleepers showed a 21-minute increase in sleep duration for the intervention group. This was associated with decreased intake of fat,

carbohydrates, and free sugars.⁴³ Perfect et al. conducted an RCT using a sleep extension in 79 adolescents with T1D. Participant retention was 100%, and sleep duration increased by one hour in 33% of participants.⁴⁴ In summary, sleep extension is feasible in both adolescents and adults and may improve glycemic control.

[figure not shown]
A.5 Wearable sleep trackers provide a critical opportunity to engage short sleepers

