Over the past few years, the public’s interest in monitoring sleep has skyrocketed, providing an important opportunity to affect sleep in public health. Marketing research reported a 500% annual growth in the wearable fitness tracker market for the past three years.⁴⁵ In 2016, over 12% of U.S. adults owned a fitness monitor,⁴⁶ and sleep was rated as the most popular feature to track.⁴⁶ Our intervention uses data from a wearable sleep tracker (Fitbit) to personalize feedback and promote interaction with remote coaches. Given that individuals often need to forgo other potentially more rewarding activities to extend sleep, sleep-tracking devices provide a way to make sleep extension insightful and rewarding. Companies including Fitbit and Apple have released features such as bedtime reminders and sleep goals. This suggests that consumers are interested in improving sleep but the impact on sleep and health is unknown.

A.6 Enhancing adherence to technology-assisted behavioral interventions is key to improvements

Many technology interventions suffer from high rates of non-adherence.⁴⁷ Coached interventions typically show

Figure 1. Supportive Accountability

larger effect sizes than unguided interventions, likely due to improved adherence.⁴⁸ The process by which human support enhances adherence to behavioral intervention technologies has been termed “Supportive Accountability,” (Figure 1),⁴⁹ which draws on broad empirical literature including clinical and organizational psychology^{50,51} and motivation theory.^{52,53} This model suggests that behavioral intervention technology users are more likely to adhere if they are accountable to another person. Accountability is defined as knowing that one will have to justify use or non-use to another individual at some future time.⁵⁰ The effects of accountability are enhanced when goal setting and progress are known to another person, goals are process- rather than outcome-focused, and expectations are defined in advance. The model involves qualities of the coach, including legitimacy (the person the user is accountable to has some expertise⁵¹ and is viewed as trustworthy and benevolent). We

designed and tested a coaching protocol around these principles⁵⁴ that demonstrated the capacity to enhance adherence in a sleep extension intervention (see C.2.8).

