C.1.3 Sleep optimization in short-sleeping non-diabetic adults resulted in improved glucose metabolism. [name] performed a randomized cross-over study using two-week behavioral sleep optimization aimed at extending sleep duration and promoting sleep hygiene, including sleep regularity, in 21 non-diabetic adults with habitual short sleep (mean 5.3h/night by actigraphy). Participants who extended their sleep duration to >6 h/night (N = 8, mean 6.6h/night) had significantly improved fasting insulin resistance (HOMA-IR; adjusted mean difference, MD, -0.50, $p = 0.013$), increased early insulin response to glucose (insulinogenic index; MD 0.39, $p = 0.001$), and improved β -cell function (disposition index; MD 1.07, $p = 0.02$).

C.1.4 Our newly developed sleep optimization intervention in adults with short sleep duration demonstrated a clinically significant median sleep increase of 35 minutes.

Table 1. Pilot trial, 6 weeks	Median sleep change	Interquartile Range Sleep change
Intervention, N = 7	+0:35:47	+0:31:14
Control, N = 3	+0:09:07	+0:32:24

The technology-assisted intervention included use of a Fitbit, weekly didactic content, interactive tools (e.g., reminders) and feedback, including graphs of the target behavior (sleep duration and regularity). The team developed and tested a coaching protocol based on behavior change

principles. Our research team conducted a randomized pilot study of 10 adult participants followed for six weeks with a protocol similar to what is proposed. Based on this experience, we refined our content and coaching protocol and assessed effects of our intervention on sleep duration at 6 weeks. All participants completed 2 periods of actigraphy. Participants in the intervention group wore the Fitbit for 85-100% of study days and completed 90% of coaching sessions. Results from the intervention ($n = 7$) and control ($n = 3$) groups showed that the intervention was effective at improving sleep duration by at least 30 min (Table 1).

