C.1.5 Our research team consists of investigators from multiple disciplines with expertise that will facilitate successful completion of the project. This application brings together an interdisciplinary team with shared (T1D, sleep, CGM technology and glycemic variability measures, chronic illness, and clinical practice) and complementary (behavioral coaching, technology-assisted behavior change, statistical modeling, and Certified Diabetes Educator [CDE®]) expertise. Collectively, the team's research strengths span conceptual, methodological, clinical, statistical, and research in self-management and chronic disease.

C.2 Research plan

		Actigraphy/ sleep questionnaire	CGM, fructosamine, HbA1c	Diabetes Distress	Feasibility/ Acceptability
20 T1D subjects	Baseline	X	X	X	
Randomization	4-week	X	X	X	
	8-week	X	X	X	X
Follow up	12-week	X	X	X	
	24-week	X	X	X	

Table 2: Study Overview

run-in phase. Subjective sleep (see C.2.3) and objective sleep assessment by wrist actigraphy (see C.2.4) will be performed. Diabetes distress will be assessed (see C.2.5). Glycemic assessments will be performed by A1C, serum fructosamine, and 1-week CGM (see C.2.6) and height, weight and waist circumference will be obtained. The participants will then be randomized 3:2 to either T1D-Sleep-Opt-In (see C.2.8) or attention control group for 8 weeks (see C.2.9). At Weeks 4 and 8, participants will have assessments of subjective and objective sleep, 1-week CGM, serum fructosamine, and diabetes distress. *Additionally, stool samples will be collected at week 0 and week 8 to measure the gut microbiome.* These measurements will be repeated at 12 for both groups- (and 24-week T1D Sleep-Opt-In only) follow-up visits to evaluate the program's durability. At the end of the intervention (Week 8), feasibility and acceptability will be determined (see C.2.7).

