C.2.6 Glycemic assessment Glycemic control will be primarily assessed by hemoglobin A1c (A1C; Quest Diagnostics), a gold standard marker of glycemic control in T1D reflecting average glucose levels in the previous 90 days. Secondary measures will include serum fructosamine (Quest Diagnostics) and CGM. Serum fructosamine is a glycated albumin that reflects glucose levels in the preceding three weeks and allows assessment of changes in glucose values in a shorter term than A1C. CGM (blinded) will be conducted using FreeStyle Libre Pro glucose sensor (FDA-approved). The sensor tracks glucose concentrations in the interstitial fluid over 24 h using a thin flexible filament (< 0.4 mm thick) inserted into the upper arm (5 mm depth). The system captures glucose levels every 1 minute and records the data every 15 minutes. Outcome variables derived from the CGM are mean glucose level, standard deviation (SD), coefficient of variation (CV), percentage of time spent < 70 mg/dl, and percentage of time spent ≥ 180 mg/dl.⁶³ Interstitial glucose measurements with FreeStyle Libre were found to be accurate compared with capillary blood glucose reference values.⁶⁴ Glycemic measures will be obtained for one week at baseline and Weeks 4, 8, 12 for both groups, (and week 24 T1D Sleep-Op-In group only). A small amount of serum or plasma (2 tsp) will be frozen and stored in a freezer at the College of Nursing for later analysis by UIC researchers.

C.2.6.1 Microbiome *Stool samples to measure the gut microbiome will be collected at week 0 and week 8. Changes in sleep may alter the gut microbiome and potentially influence glycemia. Participants will be provided a collection device (Easysampler®, ALPCO, Inc.) and return the specimen at a subsequent visit.* Remaining stool samples will be stored in a freezer at the College of Medicine for later analysis by UIC researchers.

C.2.7 Feasibility and acceptability of T1D-Sleep-Opt-In Feasibility will be determined through analysis of recruitment (number recruited, screened, eligible, and consented) and retention (% session participation, program completion rates). Acceptability will be determined through participant evaluation (written evaluation and interview at program completion). See Appendix B.

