For these pilot data, we will emphasize descriptive statistics such as means, standard deviations, effect sizes, medians, interquartile ranges, frequencies, and percentages to demonstrate the feasibility of recruitment, adherence, retention, acceptability, and treatment effects of change in outcomes between T1D-Sleep-Opt-In and attention control. Our statistical approach for a full trial of these hypotheses will be a mixed-effect model for repeated measures (MMRM), recommended for primary analysis of clinical trials with continuous endpoints.⁷³ Using this model on pilot data will allow us to assess if the statistical plan will need modification and will help with sample size calculations for a future R01 submission. Confidence intervals will be used to estimate a plausible range of values for feasibility and effect size estimates.

Sample size. This feasibility pilot study is not powered to detect significant effects for improvement in sleep, glycemic control, or diabetes distress. Our sample of 20 participants will be adequate for gaining experience using this protocol with a T1D population and for calculating mean and variability confidence intervals for sleep and diabetes-related measures.⁷⁴

References

1. National diabetes statistics report, 2017. Estimates of diabetes and its burden in the united states. 2017. <https://www.cdc.gov/diabetes/pdfs/data/statistics/national-diabetes-statistics-report.pdf>. Accessed 11/20/2017.

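### Acceptability is evaluated only at Week 8, and the available text makes no provision to ask intervention participants who withdraw earlier, so the acceptability part of Aim 1 could be too favourable

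*Combined protocol and SAP*

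**What the plan says.** Aim 1 (Specific Aims) hypothesises that "T1D-Sleep-Opt-In will be feasible and acceptable to the target population". It gives recruitment and retention as the basis for feasibility, and participant evaluation as the only basis for acceptability.

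The timing is given in three places, which agree:

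- C.2.7: "Acceptability will be determined through participant evaluation (written evaluation and interview at program completion"), followed by "See Appendix B".
- The study overview in C.2: "At the end of the intervention (Week 8), feasibility and acceptability will be determined".
- Table 2: the Feasibility/Acceptability column is marked in the 8-week row and in no other, although the 4-week row carries all the other assessments.

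C.2.7 measures retention by session participation and program completion rates, as part of feasibility. C.2.10 plans descriptive statistics including "percentages to demonstrate the feasibility of recruitment, adherence, retention, acceptability", with confidence intervals for feasibility estimates. It gives no denominator and no threshold for acceptability. The available text describes no exit interview, no evaluation at withdrawal and no recording of reasons for leaving. Appendix B was not in that text.

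**The concern.** The hypothesis is about the people the program is meant for, but the evaluation as scheduled reaches only those still in the study at Week 8. People who leave because the program does not suit them are likely to be the least satisfied, and they can say most about what should change before the larger trial. C.2.10 states that the pilot is not powered for efficacy, so Aim 1 is one of its main products. Program completion rates would show how many stopped but not why. Reasons not collected at withdrawal may be impossible to recover later.

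**Working it through.** The plan gives no dropout rate, acceptability figure or threshold, so there is no stated figure to reproduce. The check is how far an evaluation of completers only could differ from one covering everyone randomised to the intervention.

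**Inputs from the documents.** Total sample 20 (C.2.2). Allocation 3:2 (study overview in C.2). Intervention arm: 20 × 3/5 = 12. Each person who leaves without being asked is 1/12 = 8.3% of the arm.

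**Assumptions.** Between 0 and 3 of the 12 leave before Week 8. Each evaluation can be classed as favourable or not, which the plan does not define. Every completer is favourable. In the worst case, no leaver would have been.

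**Formulas.** With d leavers, the completer figure is (12 − d)/(12 − d) = 100%. The worst case over all randomised is (12 − d)/12. The largest overstatement is the difference, d/12. Intervals are exact (Clopper–Pearson) 95%.

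| Leavers | Completers only | 95% interval | Worst case over 12 | 95% interval | Largest overstatement |
|---|---|---|---|---|---|
| 0 | 12/12 = 100% | 73.5–100% | 12/12 = 100% | 73.5–100% | 0 points |
| 1 | 11/11 = 100% | 71.5–100% | 11/12 = 91.7% | 61.5–99.8% | 8.3 points |
| 2 | 10/10 = 100% | 69.2–100% | 10/12 = 83.3% | 51.6–97.9% | 16.7 points |
| 3 | 9/9 = 100% | 66.4–100% | 9/12 = 75.0% | 42.8–94.5% | 25.0 points |

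If the leavers would also have been favourable, the figure over all 12 is 100% and nothing is overstated. The last column is therefore an upper bound under these assumptions, not an expected bias.

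**What the documents say about dropout.** C.1.4 reports of the team's pilot: "All participants completed 2 periods of actigraphy". That pilot lasted 6 weeks and had 7 intervention and 3 control participants. The relevant count is 0 of 7. The exact 95% upper limit for zero events is 1 − 0.025^(1/n), so 1 − 0.025^(1/7) = 41%. A.4 cites full retention among 79 adolescents with T1D: 1 − 0.025^(1/79) = 4.6%. Both observed rates are zero. The first leaves wide uncertainty, and the second comes from a different age group.

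**Chance of at least one leaver among 12 (illustration only).** The formula is 1 − (1 − p)^12, with p assumed:

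- p = 0%: 0%
- p = 5%: 1 − 0.95^12 = 46%
- p = 10%: 1 − 0.90^12 = 72%
- p = 20%: 1 − 0.80^12 = 93%

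The expected numbers of leavers, 12p, are 0, 0.6, 1.2 and 2.4. None of the non-zero rates comes from the documents.

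**The case against.** The strongest reply is that this is silence in an incomplete text. C.2.7 points straight to Appendix B, which may contain an exit form. Program completion could also be read as calendar Week 8, so that someone who stops sessions but attends that visit is still asked. Both points stand. A reader might infer that leavers are never asked, but the documents support only the statement that the available text does not provide for it.

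A second reply is that leavers already count in Aim 1. This is right for feasibility: retention records them, and reporting it beside acceptability would partly reveal the problem. A reader might infer that Aim 1 as a whole is too favourable. The documents do not support that; only the acceptability half is exposed. Retention still gives a count without reasons.

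Third, C.2.8.4 provides weekly coaching calls that deal with barriers, so the team may already know what troubled someone who later left. That is fair, but the calls are not named as acceptability data and do not replace the evaluation.

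Fourth, the evidence in the documents points to no dropout, nothing shows that leavers would be less satisfied, and no threshold exists that a biased figure could cross. All of this stands and keeps the priority low. It does not remove the gap, because 0 of 7 over 6 weeks does not rule out a leaver among 12 over 8 weeks.

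**Conclusion.** The point holds as a low-priority design improvement. Followed as written, the schedule gives an acceptability result from those present at Week 8 for a hypothesis about the target population. The overstatement is at most 8.3, 16.7 or 25.0 percentage points with 1, 2 or 3 leavers, and zero with none. This rests on three conditions: Appendix B does not already cover early leavers, at least one of the 12 leaves before Week 8, and leavers are less satisfied than completers. The bounds also assume that all completers are favourable. With an arm of 12 the intervals are wide in any case, so the main loss would be the leavers' reasons rather than the precision of a percentage. The documents do not show that dropout is likely.

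**What to change.** Add to C.2.7:

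> The written evaluation and a short interview, including reasons for stopping where relevant, will be offered to every participant randomised to T1D-Sleep-Opt-In at Week 8 or at withdrawal from the study, whichever comes first, including those who stop sessions but remain in the study. Acceptability will be reported with the number evaluated out of the number randomised to T1D-Sleep-Opt-In, beside retention.

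If Appendix B already covers early leavers, a cross-reference in C.2.7 is enough, together with the denominator.

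The cost is two sentences and about one short call per leaver: none if nobody leaves, about 1 at an assumed 10% dropout, and 2 to 3 at 20%. Some leavers will decline, so the gap may be narrowed rather than closed, and the rating may come out less favourable. Sample size, eligibility, treatment and the efficacy outcomes are unchanged.
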